## 11. Safety

Safety assessments will include the incidence and severity of TEAEs, clinical laboratory evaluations (hematology, chemistry, coagulation, and urinalysis), vital sign measurements, ECGs, IOP measurements, and safety data collected from ocular examinations. Safety analyses will be based on the Safety Set.

### 11.1. Adverse Events

All AEs will be coded using the most recent version of MedDRA, version 25.0 or higher, and will be presented in the following data listings by SOC and PT for each subject.

- All AEs
- Ocular AEs
- AEs related to study treatment
- Serious adverse events (SAEs)
- SAEs related to study treatment
- AEs with an outcome of death
- AEs leading to study treatment discontinuation
- AEs leading to study withdrawal

Treatment-emergent adverse events (TEAEs) are AEs that began on or after the date of study treatment administration. Missing/incomplete start or stop dates associated with an adverse event (AE) will be handled as per [Section 8.3.2](#) to determine whether an AE is a TEAE. The following categories of TEAEs will be summarized by treatment arm and overall for the Safety Set using count and percentage of unique subjects experiencing a TEAE and number of events for each TEAE by SOC and PT. An overall summary table will also be produced to summarize the following categories of TEAEs.

- All TEAEs
- TEAEs related to study treatment
- Serious TEAEs
- Serious TEAEs related to study treatment
- TEAEs by maximum severity (mild [Grade 1], moderate [Grade 2], severe [Grade 3], life/sight-threatening [Grade 4], death [Grade 5]), total number of events at each severity summarized
- TEAEs by worst relationship (not related, possibly related, probably related), total number of events at each relationship summarized
- TEAEs leading to study treatment discontinuation
- TEAEs leading to study withdrawal

Summaries will be presented separately by location of the TEAEs (ocular in study eye, ocular in non-study eye, and non-ocular), and will be sorted by overall descending count of SOC and then, within a SOC, by overall descending count of PT. Subjects will only be counted once if they experience multiple events under the same SOC or PT, and at the maximum severity or worst relationship, as applicable.

This document is confidential.

Summaries by SOC and PT (not by maximum severity or worst relationship) will also include a summarization of the number and percentage of subjects with more than 1 TEAE.

Summaries of TEAEs (ocular in study eye, ocular in non-study eye, and non-ocular) by PT only will be presented by treatment arm and overall, sorted by overall descending count of PT. Subjects will only be counted once if they experience multiple events under the same PT.

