3.4 Duration of Study

Total study participation will be approximately 52 weeks (including the Screening period). After the initial Screening Visit, subjects may have between 5 and 30 days to be enrolled, at which point the study treatments/control will be administered on Day 1, if the eligibility criteria are still met. Subjects who require a longer period between initial screening and Day 1 will be re-screened prior to entry into the study. After Day 1 study treatment dosing, the follow-up period will be through 48 weeks (with visit windows of ± 7 days starting at Week 4). Eligible subjects who are enrolled in this study will be seen for the scheduled study visits over approximately 12 months depending on the time between Day 1 and the final study visit. Screen

failures will be recorded along with the reason(s) for not meeting the eligibility criteria. Study completion is achieved at the Week 48 visit (End of Study Visit).

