- d. Check central retinal artery perfusion following study injection.
- e. At Day 1: measure IOP at 10 (+/- 5) and 60 (+/- 10) minutes following the EYP-1901 dose/sham injection. If IOP measurements at any study time points are 30 mmHg or higher, two additional measurements should be performed and IOP recorded as a mean of three measurements.
- f. All CFP images will be assessed by the CRC to determine the ETDRS-DRSS scores.
- g. Spectral-domain – optical coherence tomography angiography (SD-OCTA) or swept-source – optical coherence tomography angiography (SS-OCTA) imaging to be collected at these time points at pre-specified study sites where SD-OCTA equipment is available.
- h. Clinical laboratory testing will include HbA1c, hematology, serum chemistry, coagulation, and urinalysis evaluations (refer to the study Laboratory Manual).
- i. Documented HbA1c test results dated 60 days prior to the Screening Visit will be accepted.
- j. Females of childbearing potential only. Positive urine pregnancy results will be confirmed by a serum pregnancy test.
- k. Pharmacokinetic analyses of vorolanib and X-297, its main metabolite, will be performed on blood plasma samples.
- l. Adverse events, ocular and non-ocular, will be collected from the time the informed consent is signed. However, for safety analysis, only treatment-emergent adverse events (TEAEs) will be summarized.

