7.1.7 Adverse Event Reporting

All subjects enrolled in the study will be evaluated for AEs, which will be collected from the time the ICF is signed until study completion ([Table 5-1](#)).

All AEs will be evaluated from onset until resolution or stabilization, whichever is first. Adverse events that continue after the subject's discontinuation or completion of the study will be followed until their medical outcomes are determined or until no further change in the condition is expected. The event and outcome will be reported in writing by the Investigator to the Sponsor. The Investigator shall supply the Sponsor and Institutional Review Board (IRB)/Ethics Committee (EC) with any additional requested information, notably for reported deaths.

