11.4.7 Adverse Events

Both ocular and non-ocular TEAEs are defined as events that start after the first study drug administration, and occur before termination of the study, or were present before first study drug administration and worsened after administration. Descriptive statistics will be provided for all TEAEs by treatment arm and overall for the ITT population.

Adverse events will be coded by System Organ Class (SOC) and preferred term (PT) using the current version of the Medical Dictionary for Regulatory Activities (MedDRA). Ocular and non-ocular TEAEs will be summarized separately. The number and percentage of subjects who experience an AE will be presented. Within each level of summarization (SOC, PT), subjects who experience more than one occurrence will only be counted once. Adverse events will also be presented by severity (mild, moderate, severe, life-threatening, fatal), and by relationship to study drug (not related, possibly related, probably related). Listings of deaths, SAEs, and withdrawals due to AEs will be presented.

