### **5.4. Safety Endpoints**

The safety endpoints are the rates of ocular (study eye and non-study eye) and non-ocular TEAEs at Weeks 24, 36, and 48.

This document is confidential.

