#### 8.3.2. Adverse Event Dates

In the event of a missing/incomplete start or stop date associated with an adverse event, only the treatment-emergence will be imputed using the algorithm below. Dates will not be imputed.

In general, if the missing/incomplete start date is not clearly prior to initiation of treatment, then the AE will be considered at TEAE.

If the AE end date is prior to the initiation of treatment, the AE will not be considered a TEAE.

If the AE end date is on or after the initiation of treatment:

- If the AE start date is completely missing or if the year is missing, then the AE will be considered a TEAE
- For partial AE start dates:
  - Known year, unknown month and day (or known year and day, unknown month)
    - If the year is the same as or later than the year of study drug administration, the AE will be considered a TEAE
    - Otherwise, the AE will not be considered a TEAE
  - Known year and month, unknown day
    - If the month and year are the same as or later than the month and year of the study drug administration, the AE will be considered a TEAE
    - Otherwise, the AE will not be considered a TEAE

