## **14. Changes from Analyses Planned in Protocol**

Changes from the analyses planned in the protocol include the following.

- Whereas Protocol Section 11.3.5 indicates that there will be no adjustment of analyses for covariates, secondary efficacy endpoints will include baseline value as a covariate, when applicable (SAP [Section 8.8](#)).
- The protocol defines the ITT population as all subjects who received at least one dose of study treatment and defines the efficacy population as ITT subjects who continue to at least Week 36, having the primary efficacy endpoint assessed. This SAP instead defines the FAS and Safety Set, which are both the equivalent of the protocol-defined ITT, and the PP Set, which is the equivalent of the protocol-defined efficacy population with the added criterion of subjects having no protocol deviation(s) that would significantly impact the primary endpoint. This change from the protocol in analysis set definitions is consistent with the approach taken for the EYP-1901-201 study.

This document is confidential.

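### SAP 11.1 defines TEAEs by onset date alone and, without declaring it in SAP 14, drops the protocol's limb for pre-dose events that worsen after dosing

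*SAP*

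**What the plan says.** Protocol 11.4.7 defines a TEAE by two alternative limbs. The first covers events that start after the first administration of study drug and occur before the study ends. The second covers events that "or were present before first study drug administration and worsened after administration".

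SAP 11.1 has one limb only: "Treatment-emergent adverse events (TEAEs) are AEs that began on or after the date of study treatment administration". No other section of the SAP brings the second limb back. SAP 8.3.2, which settles treatment emergence when AE dates are incomplete, works from dates alone. If the AE ended on or after the start of treatment but its partial start date falls in an earlier year, or in an earlier month, the rule is "Otherwise, the AE will not be considered a TEAE". Worsening plays no part.

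SAP 14 opens with "Changes from the analyses planned in the protocol include the following" and gives two items, covariate adjustment and analysis sets. The TEAE definition is not among them.

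The definition carries weight. SAP 5.4 says: "The safety endpoints are the rates of ocular (study eye and non-study eye) and non-ocular TEAEs at Weeks 24, 36, and 48". Protocol Table 5-1, footnote l, adds: "However, for safety analysis, only treatment-emergent adverse events (TEAEs) will be summarized".

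**The concern.** The same AE record can be a TEAE under the protocol and not under the SAP, and the programmers will follow the SAP. AEs are recorded before dosing as well as after: under protocol 7.1.7 they are those "which will be collected from the time the ICF is signed until study completion", and protocol 3.4 leaves a gap before Day 1: "After the initial Screening Visit, subjects may have between 5 and 30 days to be enrolled". An AE with a pre-dose onset is therefore an expected kind of record.

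If such an AE worsens after the injection and the site updates the existing record, it drops out of every TEAE count in SAP 11.1: all, related, serious, by maximum severity, by worst relationship, and leading to withdrawal. The serious-TEAE tables and Listing 14.3.2.2 in the SAP's index are restricted in the same way. A pre-dose event that became serious after dosing would then be visible only in the AE listings. Someone who relies on SAP 14 to learn what changed from the protocol would not know this.

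**Working it through.** The plan gives no figure to reproduce, so the check is a comparison of rules, followed by a statement of scale.

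**Classification under each document** (protocol 11.4.7 against SAP 11.1 and 8.3.2):

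| AE record | Protocol | SAP |
|---|---|---|
| Onset after dosing, during the study | TEAE | TEAE |
| Onset before Day 1, no worsening | Not TEAE | Not TEAE |
| Onset before Day 1, worsens after dosing, one record with the original onset | TEAE | Not TEAE |
| As above, but the worsening is a new record with a post-dose onset | TEAE | TEAE |
| Partial start date in a month or year before dosing, AE continues past dosing and worsens, one record | TEAE | Not TEAE (8.3.2) |
| Onset on the Day 1 date but before the injection, no worsening | Not TEAE | TEAE |

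Rows three and five are the loss. Row four shows that the loss disappears if sites open a new record. Row six shows a difference in the other direction: the SAP works by date, while the protocol requires onset after administration. The SAP also drops the protocol's upper bound at study termination. That matters little in practice, because collection stops at study completion (protocol 7.1.7). Neither of these two differences is declared either.

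**Which row a worsening falls in.** Protocol 7.1 treats worsening of a pre-existing condition as an AE. Protocol 7.1.1 makes certain ocular findings relative to the last examination AEs in their own right, and 7.1.4 does the same for laboratory abnormalities that become more severe than at baseline. Protocol 7.1.6 says that conditions present before treatment are AEs only if they worsen after treatment starts. All of this points towards row four for many worsenings. But 7.1.6 asks only for an onset date, an end date and a separate record for each distinct AE. It does not say whether a worsening of an AE already on file is distinct, or which onset date it takes. The list of AE items in 7.1.6 contains no date of severity change.

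**Scale.** Inputs: about 20 subjects per arm and about 60 in total (SAP 4.3). For one affected subject with no other TEAE in the row:

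- arm: 1/20 = 5.0 percentage points
- overall column: 1/60 = 1.7 percentage points

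If the subject already has another TEAE in that row, the subject count does not change, because SAP 11.1 counts a subject once per row. The event count would still be one short, and the subject's maximum severity could be understated.

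**The case against.** The strongest reply is that the loss may rarely occur. Under protocol 7.1.6, read alone, a condition that arises between consent and Day 1 becomes an AE only when it worsens after treatment, so its natural onset is post-dose and the SAP counts it. This stands in part. It sits in tension with protocol 7.1.7 and Table 5-1 footnote l, which have AEs recorded from consent, so pre-dose AE records will exist. It does make the loss conditional on recording practice.

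Second, protocol 11 lets the SAP modify its plans and asks for an amendment only for major changes to the primary endpoint or its analysis. That is correct. A reader might infer that the SAP breaches the protocol; it does not. The defect is an undeclared and unreconciled difference. The opening of SAP 14 does not claim a complete list, but that does not tell anyone that the TEAE definition changed.

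Third, deterioration is shown elsewhere. SAP 11.2 to 11.7 summarise laboratory values, vital signs, ECG, IOP, ocular examination and BCVA, and all AEs are listed. This limits the harm. Those summaries do not show symptoms, diagnoses, AE grade or relatedness, and they do not correct the TEAE rate.

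Fourth, SAP 8.3.2 leans towards inclusion: a start date not clearly before treatment makes the AE a TEAE. That is fair. It is the 11.1 rule carried over to partial dates, not a separate defect.

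**Conclusion.** The point holds as a contradiction between stated rules on a named safety endpoint. The mismatch in wording is certain. Its effect on the reported rates is conditional: it arises only when a pre-dose AE worsens after dosing and remains one record under its original onset. The number of such subjects cannot be derived from the documents and is probably small. The 5-point shift per affected subject assumes 20 subjects in the arm and no other TEAE for that subject in the row.

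Three stronger readings are not supported:

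- A reader might infer that post-dose worsenings in general are lost. Many will be new AEs with a post-dose onset, and these are counted.
- A reader might infer that the SAP simply narrows the definition and so lowers TEAE rates. It also widens it on Day 1 and drops the upper bound, so the net direction is not fixed by the text.
- A reader might set the 5 to 30 days before Day 1 against the 336 days of follow-up and take the ratio as a rate. It is a ratio of calendar windows. It says nothing about how many events persist, worsen and stay as one record, and the window is not strictly bounded, since recording starts at consent and subjects can be re-screened.

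The primary endpoint is untouched, and SAE reporting to the sponsor (protocol 7.1.7.1) does not depend on the TEAE definition.

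**What to change.** 1. In SAP 11.1, keep the onset rule at date level and add a second limb for AEs present before study treatment that worsened after it. Do not replace the sentence with the protocol's wording wholesale. Protocol 7.1.6 asks for onset dates, not times, so a rule that needs onset after the injection could not reliably classify Day 1 events.
2. State how a post-dose worsening of a pre-dose AE is identified: by a new AE record dated at the worsening, or by a masked review, before lock, of AE records with a pre-dose onset. A dated severity-change flag is not among the AE items in protocol 7.1.6, so the rule should not depend on one.
3. Add the same exception to SAP 8.3.2, so that a pre-dose partial start date alone does not make a worsened AE non-treatment-emergent.
4. List the remaining differences from protocol 11.4.7 in SAP 14: the date-level onset rule and the missing bound at study termination. If the sponsor prefers to leave out the worsening limb, that choice should be declared and justified there.

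The cost is a few sentences of SAP text and a small record check before lock, done by staff who are still masked after the Week 36 readout. TEAE rates may come out slightly higher. No visit, assessment or sample size changes.

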6.6.4 Permitted Medication and Procedures

Following the intravitreal injections of either dose of the EYP-1901 insert (2060 µg or 3090 µg) on Day 1, treatment of the fellow eye will be at the discretion of the Investigator. Any fellow eye therapy should be documented in concomitant meds during the study if required.

After Day 1, all subjects, regardless of treatment assignment, may receive approved anti-VEGF supplemental therapy or other standard of care therapy if they have ocular diabetic complications

warranting intervention. All ocular diabetic complications in the study eye will be managed in accordance with each study center's standard of care and must be documented as an AE.

During the study, participants who develop ocular diabetic complications in the study eye requiring anti-VEGF treatment per standard of care may be administered therapy as required. If needed, the study centers will provide their own supply of FDA-approved anti-VEGF therapy and submit the associated costs for reimbursement. The number of anti-VEGF injections received, the name of the product being injected, and the timing of all injections must be recorded in the source documents and eCRF.

Participants who develop ocular diabetic complications requiring PRP or retinal laser standard of care must have the time of laser treatment recorded in the source documents and eCRF.

Participants who develop ocular diabetic complications requiring surgical intervention standard of care (eg, pneumatic retinopexy, cryopexy, scleral buckle) must have the type of intervention and the time of intervention recorded in the source documents and eCRF.

In this case, the Investigator is required to contact the Medical Monitor prior to administering treatment if feasible.

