- Progressive disease (NPDR) is expected and will not be considered an SAE.

Clarification of SAEs:

- Death is an outcome of an AE, and not an AE in itself.
- All deaths, regardless of cause or relationship, must be reported.
- Complications that occur during hospitalizations are AEs. If a complication prolongs hospitalization, it is an SAE.
- “In-patient hospitalization” means the subject has been formally admitted to a hospital for medical reasons for any length of time. This may or may not be overnight. It does not include presentation to, and/or care within, an emergency department.
- The Investigator should attempt to establish a diagnosis of the event based on signs, symptoms, and/or other clinical information.

Note: Progressive disease should be recorded on the AE eCRF. However, because it is expected in the study population, it will not be considered as an SAE.

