7.1.5 Adverse Event Severity and Relationship

Adverse event severity is defined as a qualitative assessment of the intensity of an AE as determined by the Investigator. The assessment of severity is made irrespective of the relationship or seriousness of the event to EYP-1901, sham, or the injection device.

In the absence of an assigned severity per the CTCAE version 5.0 or higher ([Appendix 4](#)) grading criteria, the Investigator will grade AEs according to the following severity criteria:

Mild/Grade 1: The event may be noticeable to subject; does not influence daily activities; usually does not require intervention.

Moderate/Grade 2: The event may be of sufficient severity to make subject uncomfortable; performance of daily activities may be influenced; intervention may be needed.

Severe/Grade 3: The event may cause severe discomfort; usually interferes with daily activities; subject may not be able to continue in the study; treatment or other intervention usually required.

Life- or Sight-Threatening/Grade 4: The event requires urgent intervention to preserve life and/or permanent loss of vision.

Death/Grade 5: The event resulted in the subject's death.

Causality/Relationship to Study Treatment

The relationship of study treatment (ie, EYP-1901 or sham), the applicator, or the injection procedure, to each AE must be determined by the Investigator according to the following:

Not Related: Evidence indicates no plausible direct relationship to the study treatment, device, or procedure, or there is a reasonable causal relationship between non-study product, concurrent disease, or circumstance and the AE; and/or a causal relationship is considered biologically implausible.

Possibly Related: There is a reasonable causal relationship between the study treatment, device, or procedure and the AE. There may or may not be a clinically-plausible temporal sequence between the onset of the AE and study treatment, device, or procedure; the AE is not reasonably supported by other conditions.

Probably Related: The study treatment, device, or procedure and AE occurrence are reasonably related in time; a clinically-plausible temporal sequence between the onset of the AE and study treatment, device, or procedure is likely; based upon the Investigator's clinical experience, the association of the AE with study treatment, device, or procedure is likely; all other potential causes have been ruled out.

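### Study-eye ocular TEAE totals combine diabetic complications and progression with all other ocular events, so a treatment benefit can offset an excess of other events in the aggregate rows

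*SAP*

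**What the plan says.** Two protocol rules put disease outcomes into the AE data. In Section 6.6.4 the sentence on complications begins "All ocular diabetic complications in the study eye will be managed in accordance with" each centre's practice and ends "standard of care and must be documented as an AE". Section 7.1.2 adds: "Note: Progressive disease should be recorded on the AE eCRF". The same section limits seriousness: "Progressive disease (NPDR) is expected and will not be considered an SAE". The first rule is mandatory and covers the study eye. The second is worded as an expectation.

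SAP 5.4 sets the safety endpoint: "The safety endpoints are the rates of ocular (study eye and non-study eye) and non-ocular TEAEs at Weeks 24, 36, and 48". SAP 11.1 defines a TEAE by its start date alone and makes no exception for disease events. It summarizes TEAEs by arm "using count and percentage of unique subjects experiencing a TEAE and number of events for each TEAE by SOC and PT", separately for study eye, non-study eye and non-ocular events. There are further tables by maximum severity, worst relationship, relatedness and seriousness, and by preferred term alone. No entry in the SAP table index (the 14.3.1 series) groups diabetic complications or progression, or removes them.

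The overlap with efficacy is explicit. SAP 10.2 builds its CI-DME endpoint and both macular edema definitions from AE preferred terms, so one AE record can count in an efficacy table and in a TEAE table.

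**The concern.** Characterizing safety is the first secondary objective listed in both documents. A reader who wants to know whether the insert causes ocular harm will look first at the share of study-eye subjects with any ocular TEAE, then at the SOC and maximum-severity rows. Each of these counts a subject who progressed or had a diabetic complication alongside a subject who had, for example, inflammation or an injection-related event. The more the drug prevents the first kind of event, the more room there is for the second kind without any change in the total.

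The subject-level rate of other ocular TEAEs cannot be recovered from the printed counts. Three preferred-term rows with one subject each may be one subject or three, and SAP 11.1 counts a subject once within each SOC or preferred term. With about 20 subjects per arm, an excess spread thinly over several terms would show best in an aggregate, and that aggregate is the row that is mixed.

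**Working it through.** **Inputs.** About 20 subjects per arm (SAP 4.3; 3 x 20 = 60). The documents state no AE rate, alpha, power or effect size, so there is no figure in the plan to reproduce. All event rates below are assumptions, shown over a range.

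**Formula.** Let d be the probability of at least one disease TEAE (progression or diabetic complication) and o the probability of at least one other ocular TEAE in the study eye. If the two are independent within a subject, P(any ocular TEAE) = 1 - (1 - d)(1 - o).

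**Fixed assumption.** o = 10% on sham and 30% on active, a true excess of 20 points. The last column is the exact probability, from two independent binomials with n = 20, that the active arm shows more affected subjects than sham.

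| Disease TEAEs, sham / active | Any ocular TEAE, sham | Any ocular TEAE, active | Difference (active minus sham) | P(active count > sham count) |
|---|---|---|---|---|
| 20% / 20% | 1 - 0.80 x 0.90 = 28.0% | 1 - 0.80 x 0.70 = 44.0% | +16.0 points | 0.82 |
| 20% / 10% | 28.0% | 1 - 0.90 x 0.70 = 37.0% | +9.0 | 0.67 |
| 30% / 10% | 1 - 0.70 x 0.90 = 37.0% | 37.0% | 0.0 | 0.44 |
| 40% / 10% | 1 - 0.60 x 0.90 = 46.0% | 37.0% | -9.0 | 0.23 |
| 50% / 10% | 1 - 0.50 x 0.90 = 55.0% | 37.0% | -18.0 | 0.09 |

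With disease events excluded, the comparison is 10% against 30% in every row, and the same probability is 0.93.

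The first row has no treatment benefit, so its loss of 4 points is plain dilution. The offset in the later rows comes from the benefit.

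**Other assumed excesses.** With other events at 10% against 25%, the 15-point excess appears as +12.0, -4.5 and -22.5 points in the first, third and fifth scenarios. With 20% against 40%, the 20-point excess appears as +16.0, +2.0 and -14.0.

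**Which arm moves.** Hold sham at d = 30% and o = 10%. Its rate is 37.0% whatever the drug does. With no toxicity (o = 10% on active), the active rate is 37.0%, 28.0%, 19.0% or 10.0% as its disease rate is 30%, 20%, 10% or 0%. The contrast shifts because the active rate falls.

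**Precision.** Power to detect 10% against 30% with 20 per arm at two-sided 0.05 is about 0.35, so even the separated rate is descriptive.

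**The case against.** The strongest reply is that the SAP already separates events in several ways. Study-eye TEAEs are tabulated by SOC and preferred term and by preferred term alone, and the related, serious, maximum-severity and worst-relationship tables also run down to preferred term. A distinctive toxicity term therefore keeps its own row by arm. IOP (SAP 11.5), slit-lamp and ophthalmoscopy findings (11.6), and letter-loss proportions with differences from sham (11.7) give further views. Macular edema AEs and vision-threatening complications are shown by arm under SAP 10.2, and an ocular AE listing (16.2.7.2) would let someone recount by hand. No test of TEAE rates is planned. The total is also a valid randomized comparison of all ocular events.

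Most of this stands, and it confines the point to the aggregate rows and to terms that could be either disease or a drug or procedure effect. It does not remove the point. No printed row gives the subject-level rate of other ocular TEAEs, and a recount from the listing would classify terms after treatment is known unless the list is fixed first. The relatedness tables help only in part: Protocol 7.1.5 allows a not-related judgment where concurrent disease explains the event, which is often arguable in a diabetic eye.

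A second reply concerns the remedy. A term list cannot tell a diabetic vitreous hemorrhage or macular edema from one caused by the drug or the injection, so a disease group could absorb real harm. That is correct, and the fix has to deal with it.

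**Conclusion.** The point holds for the any-ocular-TEAE, SOC-level and maximum-severity rows in the study eye. Under the assumed 10% against 30%, the pooled difference runs from +16 to -18 points depending on the disease rates. These figures rest on assumed rates and on independence of the two kinds of event. They show that an offset or reversal is possible, not that it will occur.

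A reader might infer more than the documents support:

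- That an effective drug raises the sham TEAE rate. It does not; the active rate falls.
- That ocular toxicity is hidden in the safety package as a whole. The preferred-term rows and the other ocular tables keep distinct toxicity visible.
- That every progression must be reported. The mandatory rule covers study-eye complications; the progression rule uses weaker wording.
- That the serious-TEAE table is mixed in the same way. Protocol 7.1.2 keeps progression out of SAEs. Some complications could still enter through the sight-threatening criteria in 7.1.3, so that table is less exposed, not immune.
- That relationship to applicator and procedure is left out of the tables. Protocol 7.1.5 defines each relationship category against treatment, device or procedure, so the documents do not show an omission.

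This is an inexpensive improvement to reporting. It does not affect the validity of the primary analysis.

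**What to change.** Keep every existing table. Add to SAP 11.1 one study-eye TEAE summary by arm, overall and by maximum severity, counting subjects once within each of two groups:

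- (a) diabetic progression and complication preferred terms;
- (b) all other ocular TEAEs.

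Have the masked ophthalmology reviewers, who already classify medication and procedure terms under SAP 10.2, fix the term list before the Week 36 unmasking described in SAP 2.2 and 13. Flag the terms that can be either disease or a drug or procedure effect, such as vitreous hemorrhage and macular edema, and show them in both groups, so that no possible harm drops out of (b). A footnote should state that the groups overlap on those terms and that the display is descriptive.

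The cost is a paragraph of SAP text, a term list and a few rows or one table from data already collected, with no protocol change. The remaining limitation is that flagged terms stay ambiguous, so group (b) will still carry some disease events.
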